## **10. Concomitant Treatment**

Concomitant medications that are exclusionary include:

- Use of sex hormones for treatment
- Use of androgens or other compounds for body building
- Use of retin-A or Accutane for the treatment of acne

Concomitant medications are discouraged except as prescribed for the treatment of co-existing medical conditions. All concomitant treatments will be recorded on the subject's case record form (CRF), including the generic name of the drug, start and stop dates, and reason for use.

## **11. Study Materials**

### **11.1 Study Medication**

Each subject will receive the study drug Isotretinoin 20 mg twice daily for 32 weeks. The first dose will be administered at the clinic under the observation of the study staff. The day and time of the start of treatment will be recorded on the CRF in the appropriate space provided. The subjects will be given enough supply of medication until their next visit.

A Study drug log (diary) will be provided to the subjects for recording the times of taking study medication. These drug logs will be reviewed at each visit. The investigator will retain the copies of these logs as source documents.

The prescriber [name], is registered in iPLEDGE. All subjects will be registered in iPLEDGE and undergo the extensive counselling recommended by this program.

### **11.2 Storage**

Study drug will be stored at a temperature not to exceed 25°C in a locked storage area at the study site. The study drug will be accessible only to study personnel designated to handle study drug.

### **11.3 Disposal**

Empty used pill bottles will be returned to the clinic and retained at the site in a locked storage area. All unused study drug will be returned to the University of Washington investigational pharmacy for destruction once final drug accountability has been performed.

## **12. Study Procedures**

### **12.1 General**

The study will consist of 3 periods:

1. Pre-treatment period (including screening) for up to 60 days.
2. Treatment period for 32 weeks
3. Recovery period of 24 weeks

The treatment period will begin with Day 1 of treatment, twice daily for 32 weeks. The recovery period will last for 24 weeks.

### **12.2 Laboratory Samples**

Blood samples for laboratory analyses will be collected at the first screening visit, and at the treatment visits on weeks 8, 16, 24, 32 and 56 with the subject in a fasting state (no food or drink other than 4 to 6 ounces of water or non-sweetened clear liquids for a minimum of 8 hours). A snack will be provided after the blood is drawn. If the subject is in a non-fasting state, the investigator will reschedule the visit within two days. The investigator will review all laboratory reports and file a copy with each subject's chart and CRFs. The CBC and blood chemistry samples will be analysed at the local hospital laboratory at the University of Washington.

The serum samples for measurements of retinoic acid will be frozen for analysis at the end of study. In terms of processing, the blood samples will be collected into vacutainers (containing serum separating tube gel and clot activator) wrapped aluminum foil to prevent light exposure that can degrade retinoic acid, and gently mixed. The samples will be allowed to clot for 30 minutes at room temperature before centrifugation at 1000-2000g for 15 minutes. Following centrifugation, the serum samples will be frozen in (light protection?) tubes at -80 C.

**Semen Analysis:** Semen will be collected after at least 48 hours of abstinence from ejaculation at the two screening visits, treatment visits 2-9, and all follow up visits. The semen will be assessed for the presence of sperm, and, if present, for count and motility. In addition, a known volume of semen will be diluted and washed for making smears for morphology assessments. These

procedures allow for accurate total sperm count and motility assessments following the WHO protocol (18).

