Study Design	
We will conduct an unblinded, pilot study to determine the impact of therapy with 13-cis retinoic acid on sperm indices in azoospermic men. Twenty azoospermic men, ages 21-60 will be enrolled in a 32-week study of 20 mg twice daily of 13-cis retinoic acid. The subjects will be closely followed for side effects related to treatment. The impact of treatment on the appearance of sperm in the ejaculate will be determined by monthly seminal fluid analyses.
 
All aspects of this study will be performed in compliance with Good Clinical Practice (GCP) regulations, ICH guidelines, the Declaration of Helsinki, and under an FDA Investigational New Drug (IND) application.

Number of Subjects	Twenty men.
Duration of Trial	Enrollment should be completed in about 18 months, resulting in total study duration of about 36 months including screening, treatment phase, end of study visit procedures, close out and data analysis.
Duration of Treatment	The active treatment phase will be 32 weeks.
Dosage and Regimen	13- cis retinoic acid at 20 mg twice daily with meals for 32 weeks.
Inclusion Criteria	Subjects will be infertile men with azoospermia on at least two semen analyses separated by at least one week and no pregnancy with partner with normal cycles and normal hysterosalpingogram despite >1 year of unprotected intercourse.
Exclusion Criteria	Exclusion criteria include: hypogonadotropic hypogonadism (that might respond to gonadotropin injections), the use of anabolic steroids, illicit drugs, or the consumption of more than 4 alcoholic beverages daily, severe mental health problems, or current therapy with retinoic acid (e.g. Accutane) or vitamin A.
Efficacy Parameters	The appearance of sperm in the ejaculate during treatment
Safety Parameters	
 
• CBC, clinical chemistry panel (glucose, liver and renal function tests including urea, creatinine, albumin, calcium alanine aminotransferase, aspartate aminotransferase, alkaline phosphatase, bilirubin), CK, full lipid panel
 

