	
including: Total cholesterol, HDL, LDL and fasting triglycerides at baseline, week 8, 16, 24 and 32 of treatment, and study exit. Additional measures will be conducted if any abnormal values are found until the end of study visit.
 
 
• Adverse event and concomitant medications throughout the study. Other safety parameters include vital signs; and changes in pre- and post-treatment physical examination results and score on the PHQ9 depression questionnaire.
 

Evaluations	
The following determinations will be made in all subjects:
 
 
• Semen analysis will be collected twice during screening and every four weeks during treatment and twice during recovery
 
• Serum samples will be collected for the measurement of: vitamin A, all-trans and 13-cis retinoic acid, testosterone, FSH and LH. Serum for these measures will be collected before the beginning of the treatment, and every two months during treatment and sy study exit.
 

Other Assessments	
Demographic characteristics, including age and race, will be collected.

Statistical Analysis	
The primary endpoint is the appearance of sperm in the ejaculate of treated men between baseline and 32 weeks. This analysis will be conducted using a Wilcoxon signed-rank test.

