## **5. Study Design**

We will conduct an open-label pilot trial to determine the impact of therapy with 13-*cis* retinoic acid on sperm indices in infertile men. Twenty infertile men with azoospermia will be enrolled in a 32-week study of 20 mg twice daily of 13-*cis* retinoic acid. The subjects will be closely followed for side effects related to treatment. The impact of treatment on indices of spermatogenesis will be determined by monthly seminal fluid analyses.

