## **9. Selection of Subjects**

### **9.1.1 Inclusion Criteria**

1. Subjects will be infertile men (no pregnancy with partner with normal cycles and normal hysterosalpingogram despite >1 year of unprotected intercourse).
2. Azoospermia (no sperm apparent in centrifuged semen) as assessed by semen analysis on two occasions separated by one week.
3. In the opinion of the investigator, is able to comply with the protocol, understand and sign an informed consent and HIPAA form.

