#### **12.3.1 Screening Visit 1**

The following screening procedures will be performed at the first screening visit:

- Each participant must sign an IRB-approved informed consent form before any of the study-related procedures can be performed. The original signed informed consent form will be kept on file by the investigator with the subject's record and a copy will be given to the subject.
- Subjects will also complete an Isotretinoin-specific consent form as provided by the iPLEDGE program
- A general medical history will be taken and will include information on current and previous diseases and treatment.
- Vital signs (pulse, blood pressure) will be taken and recorded.
- Complete physical exam, including measurement of testicular volume, will be performed.
- Fasting blood samples will be obtained for the following measurements: Complete blood count (CBC), clinical chemistry including glucose, liver and renal function tests (urea, creatinine, albumin, alanine aminotransferase, aspartate aminotransferase, gamma glutamine transferase, alkaline phosphatase), creatine kinase (CK), bilirubin, albumin, full lipid panel including total cholesterol, HDL, and LDL, triglycerides, hematology (hematocrit, hemoglobin), and hormones (LH, FSH, T)
- Semen analysis will be done to determine if sperm are present
- Height and weight will be collected
- Participants will be questioned regarding past? And concomitant medications and adverse events.
- Once lab results are obtained and considered consistent with idiopathic infertility from azoospermia by the investigator as per the inclusion/ exclusion criteria for enrollment, the

participant is informed by telephone of his lab results. If conformance to the inclusion/exclusion is confirmed, he is scheduled to return to the clinic for the 2nd sperm collection one week later.

- 

### 12.3.2. Screening Visit 2

Vital signs (pulse, blood pressure) will be taken and recorded.

- Participants will be questioned regarding concomitant medications and adverse events.

If this 2nd sperm collection also meets enrollment criteria, the subject is scheduled to begin on treatment.

- If any results are abnormal, according to local laboratory standards and in the clinical judgment of the investigator, the subject will be informed and excluded from the study and referred to his primary physician.

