## 14. Statistical Considerations

**Data analysis and Interpretation of Results:** The primary endpoint is the presence of sperm in the ejaculate at week 32 of treatment compared with its absence at baseline. The presence of sperm after 32 weeks of treatment will be compared with baseline using a Wilcoxon sign-rank test. Linear regression will be performed to determine if significant relationships between baseline (or delta) serum concentrations of 13-cis retinoic acid and changes in sperm quality are present using STATA Version 10.0 (College Park, TX, USA). For all comparisons, an alpha of 0.05 will be considered significant.

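### Sperm present or absent is the primary endpoint, but the protocol specifies neither masking of the reader to visit nor the same centrifuged preparation at every visit

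*Combined protocol and SAP*

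**What the plan says.** The trial has one arm and is not blinded. The Synopsis states: "We will conduct an unblinded, pilot study to determine the impact of therapy". Section 5 says the same in other words: "We will conduct an open-label pilot trial to determine the impact of therapy".

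Three parts of the protocol govern the endpoint reading.

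- **Entry.** Section 9.1.1, criterion 2, requires: "Azoospermia (no sperm apparent in centrifuged semen) as assessed by semen analysis on two occasions separated by one week". Section 12.3.2 makes the screening reading decide enrolment: if the second "sperm collection also meets enrollment criteria, the subject is scheduled to begin on treatment".
- **Reading.** Section 12.2 covers the two screening visits, treatment visits 2 to 9 and the follow-up visits with one instruction: "The semen will be assessed for the presence of sperm, and, if present, for count and motility". It then describes smears for morphology and refers to a WHO protocol for count and motility. Sections 12.4.2 and 12.4.3 again ask for presence of sperm. None of these sections mentions centrifuging semen.
- **Endpoint.** Section 14 states: "The primary endpoint is the presence of sperm in the ejaculate at week 32 of treatment compared with its absence at baseline". The Synopsis is looser: "The primary endpoint is the appearance of sperm in the ejaculate of treated men between baseline and 32 weeks". The first is one reading per man. The second can be read as any of eight.

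No section identifies the reader, says what the reader is told about a specimen, or provides for coding, a fixed search or a second reading.

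**The concern.** Presence or absence of sperm at the limit of detection is a judgement, and it can shift with what the reader expects. Here the expectations at the two ends of the comparison point the same way. A negative reading at screening moves a man towards enrolment, and a positive reading on treatment makes him a responder. Every enrolled man starts at absent, so change can only be upward, and there is no control arm in which the same error would cancel.

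The preparation is a second gap. If baseline absence is established on centrifuged semen and later samples are handled differently, the two readings are not comparable, whichever way the difference runs.

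Giving the drug open-label does not require open reading of the semen, because the laboratory needs only the specimen. The trial therefore leaves unguarded a source of error that it could reduce cheaply.

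**Working it through.** **Inputs.** N = 20, drop-out 10%, response rate 15%, alpha 0.05 (section 14.1). Two screening, eight treatment and two follow-up semen samples per man (section 12.2). Wilcoxon signed-rank test against baseline (section 14). Enrolment over about 18 months (section 6). Up to 50 men screened (section 7).

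**The plan's own figure.** Section 14.1 claims 80% power but gives no null rate, so the figure cannot be reproduced. With 18 men and a true rate of 15%, the chance of at least one responder is 94.6% and of at least two is 77.6%. Nothing below depends on the 80%.

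**Weight of one man.**
- Evaluable men: 20 × (1 − 0.10) = 18.
- Responders at the target rate: 0.15 × 18 = 2.7.
- One misclassified man: 1/18 = 5.6 percentage points, or 1/2.7 = 37% of the target rate.

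**How few positives decide the test.** With every baseline absent, r responders give r equal positive changes and no negative ones, so z = √r. Three responders give two-sided p = 0.083 and four give p = 0.046. The exact two-sided version, p = 2 × 0.5^r, needs six (p = 0.031).

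**What reading error could do.** The documents give no error rate, so the rates e below are assumptions. With no drug effect and independent readings, a man is falsely positive with probability e if only week 32 counts, and 1 − (1 − e)^8 if any of eight visits counts. Binomial results for 18 men:

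| Assumed e per reading | ≥1 false responder, week 32 | ≥1, any of eight | ≥4, week 32 | ≥4, any of eight |
|---|---|---|---|---|
| 1% | 16.5% | 76.5% | <0.1% | 4.5% |
| 2% | 30.5% | 94.5% | <0.1% | 27.7% |
| 5% | 60.3% | 99.9% | 1.1% | 90.3% |
| 10% | 85.0% | >99.9% | 9.8% | 99.9% |

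On the week-32 definition, low error rates can create a stray responder but rarely a significant test. On the any-visit reading the exposure is much larger. Coding lowers only the part of e that comes from expectation.

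**What coding cannot reach.** Assume a man has sperm detectable in 10% of samples regardless of drug. He passes both screens with probability 0.9² = 81%, and then shows sperm at least once in eight samples with probability 1 − 0.9^8 = 57%. A perfectly masked reader would record the same.

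**How well visits would mix.** Treatment samples number up to 20 × 8 = 160 and follow-up samples 20 × 2 = 40. Screening samples number at most 50 × 2 = 100. This is a ceiling, because under section 12.3.1 only men who pass the first visit return for a second sample. The earliest specimens can only be screening samples. If enrolment is even over 18 months (about 78 weeks), about 32/78 = 41% of week-32 specimens arrive after screening has ended, and these can mix only with other treatment or follow-up samples.

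**The case against.** The strongest reply is that the documents do not say the reader is unmasked. Unblinded and open-label describe the treatment, and the protocol is silent about the laboratory. That is correct: a reader might infer an unmasked reader, but the text supports only that masking is not specified. The gap remains, because nothing in the plan keeps the visit from the reader.

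A reader might also infer that one slide under-read at screening becomes a response. It does not. Entry needs two negative samples, and a response needs a later positive at a visit that counts.

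Nor do the documents show that every difference in assessment favours the drug. If treatment samples were not centrifuged, detection on treatment would be lower, which works against it. The protocol does not say they are uncentrifuged either. Section 12.2 covers screening and later samples alike and names no centrifugation for any of them, so the gap is one of specification.

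The cited WHO protocol may already fix the search. Section 12.2 invokes it for count and motility, and whether it also governs the search for presence cannot be settled from these documents. A positive reading is also followed by count, motility and morphology, which gives some check on an over-call but none on missed sperm.

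Finally, 5.6 points is the weight of any one man for any reason and does not measure the bias. That stands.

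**Conclusion.** The point holds as a gap in specification with a cheap remedy. The primary endpoint is a present-or-absent reading in an uncontrolled open-label trial. Masking of the reader to visit is not specified, and centrifuged semen is named for inclusion only. The target response rate corresponds to 2.7 of 18 men, so each misclassified man shifts the estimate by 5.6 points. This rests on the 10% drop-out in section 14.1. The size of any reading error is unknown, and the tabulated rates are assumptions.

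It would be tempting to conclude that coding removes the bias. It only reduces reader expectation, and common handling only reduces preparation differences. Visits are partly mixed in time at best. Intermittent sperm, selection on two negative samples and the lack of a control arm all remain. No sample size, alpha or power figure changes.

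**What to change.** Add a paragraph to section 12.2 stating that:

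- every semen specimen (screening, treatment and follow-up) carries a code that shows neither visit nor treatment status;
- every specimen is prepared by the same centrifuged method and examined with the same fixed search;
- the existing laboratory staff report sperm present or absent before the coordinator links the code to the man and visit;
- screening specimens are still read in real time, with the coordinator applying the result to eligibility after linking.

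Appendix 1 also marks a semen analysis at T1, which sections 12.2 and 12.4.1 do not list. If that sample is taken, the same paragraph should cover it. The paragraph works under either statement of the endpoint, but the week-32 and between-baseline-and-week-32 definitions should be reconciled so that it is clear which readings count.

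The cost is coded labels and a small labelling and linking task for the coordinator. No additional reader, sample or visit is needed.

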### **12.3 Visits in Pre-treatment period**

All visits will be scheduled between 7:00am and 3:00pm.

#### **12.3.1 Screening Visit 1**

The following screening procedures will be performed at the first screening visit:

- Each participant must sign an IRB-approved informed consent form before any of the study-related procedures can be performed. The original signed informed consent form will be kept on file by the investigator with the subject's record and a copy will be given to the subject.
- Subjects will also complete an Isotretinoin-specific consent form as provided by the iPLEDGE program
- A general medical history will be taken and will include information on current and previous diseases and treatment.
- Vital signs (pulse, blood pressure) will be taken and recorded.
- Complete physical exam, including measurement of testicular volume, will be performed.
- Fasting blood samples will be obtained for the following measurements: Complete blood count (CBC), clinical chemistry including glucose, liver and renal function tests (urea, creatinine, albumin, alanine aminotransferase, aspartate aminotransferase, gamma glutamine transferase, alkaline phosphatase), creatine kinase (CK), bilirubin, albumin, full lipid panel including total cholesterol, HDL, and LDL, triglycerides, hematology (hematocrit, hemoglobin), and hormones (LH, FSH, T)
- Semen analysis will be done to determine if sperm are present
- Height and weight will be collected
- Participants will be questioned regarding past? And concomitant medications and adverse events.
- Once lab results are obtained and considered consistent with idiopathic infertility from azoospermia by the investigator as per the inclusion/ exclusion criteria for enrollment, the

participant is informed by telephone of his lab results. If conformance to the inclusion/exclusion is confirmed, he is scheduled to return to the clinic for the 2nd sperm collection one week later.

- 

### 12.3.2. Screening Visit 2

Vital signs (pulse, blood pressure) will be taken and recorded.

- Participants will be questioned regarding concomitant medications and adverse events.

If this 2nd sperm collection also meets enrollment criteria, the subject is scheduled to begin on treatment.

- If any results are abnormal, according to local laboratory standards and in the clinical judgment of the investigator, the subject will be informed and excluded from the study and referred to his primary physician.
- Subjects will be informed that they cannot donate blood during treatment and for 12 weeks after treatment is completed.

## 12.4 Visits in treatment period

Nine visits will occur in the treatment period: week 0, week 4, week 8, week 12, week 16, week 20, week 24, week 28 and week 32. All visits are  $\pm 6$  (does this include one week later?) eg following Tuesday?days.

### 12.4.1 Visit 1 (week 0)

This is the day 1 of treatment. The following will be done at this visit:

- Vital signs (pulse, blood pressure) and weight will be taken and recorded.
- Subjects will be questioned regarding concomitant medications and adverse events. If the subject is taking a medication that is listed as disallowed the subject should not be enrolled in the study.
- The subject will complete the PHQ9 questionnaire (see appendix 5)
- Subjects will be given enough supply of study medication for 30 days. This doesn't allow enough medication, in case subject has to come in at week 4 + 6 days.

- A study drug log will be dispensed to record the date and time of administration of the study drug. Subjects will be instructed to take the study drug twice a day, except on the day of the visit. Subjects will be scheduled to return to the clinic after 28 +/- 6 days.

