#### **12.4.2 Visits 2-9 (Treatment Visits)(+/- 6 days)**

These visits are for weeks 4, 8, 12, 16, 20, 24, 28 and 32. The following procedures will be done at these visits:

- Vital signs (pulse, blood pressure) and weight will be taken and recorded.
- The subject will complete the PHQ9 mood questionnaire
- Complete physical exam including and testicular examination and volume measurement will be performed.
- Subjects will be questioned regarding concomitant medications and adverse events.
- Any unused study drug counted for drug accountability and returned to subject? At treatment visit 32 or early exit visit, all unused study drug will be collected.
- Study drug log will be reviewed to check the date and time of drug administration. These logs will be collected at each treatment visit.
- A blood sample will be drawn at week 8, 16, 24 and 32. The time of day of the blood draws will be recorded in the source document.
- A semen sample will be obtained for the presence of sperm, and, if present, the measurement of sperm count, concentration, motility and morphology
- Fasting blood samples will be obtained for the following measurements: CBC, clinical chemistry including glucose, liver and renal function tests (urea, creatinine, albumin, calcium, alanine aminotransferase, aspartate aminotransferase, gamma glutamine transferase, alkaline phosphatase, bilirubin, and albumin), creatine kinase, full lipid panel including total cholesterol, HDL and LDL, triglycerides, hematology (hematocrit, hemoglobin), and testosterone, FSH and LH at weeks 8, 16, 24, and 32.
- In addition, blood samples will be collected at each visit for two serum samples to be frozen for the future analysis of serum retinoid levels.
- Subjects will be scheduled to return to the clinic for follow-up visits.
- Subjects will be given the next month's supply of study drug at visits 2-8 (weeks 4, 8, 12, 16, 20, 24 and 28).

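### The 30-day first supply does not reach the end of the 28 +/- 6 day return window, so a man returning late but in window can be without drug for up to 3 to 4 days.

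*Combined protocol and SAP*

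**What the plan says.** Section 12.4.1 sets the first supply: "Subjects will be given enough supply of study medication for 30 days". The next sentence, which reads as a drafting comment left in the text, says: "This doesn't allow enough medication, in case subject has to come in at week 4 + 6 days". The 30-day figure was not changed. The same section sets the return visit: "Subjects will be scheduled to return to the clinic after 28 +/- 6 days". Sections 12.4 and 12.4.2 also give a window of 6 days either side. A query about its meaning is still embedded in 12.4, but the number is the same throughout.

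Section 11.1 gives the general rule: "The subjects will be given enough supply of medication until their next visit".

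Two statements bear on how fast the first supply is used. Section 11.1 says "The first dose will be administered at the clinic under the observation of the study staff", while 12.4.1 says "Subjects will be instructed to take the study drug twice a day, except on the day of the visit". Neither says whether the observed dose comes out of the 30-day supply.

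The next dispensing is at Visit 2, where 12.4.2 says "Subjects will be given the next month's supply of study drug at visits 2-8", with no number of days. No interim refill is described anywhere.

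**The concern.** For a late return within the window, the 30-day supply, the 34-day limit and the promise in 11.1 cannot all hold. Treatment is meant to be twice daily for 32 weeks, and here the dispensing rule itself can interrupt it in a man who keeps to the schedule.

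Three things are at stake, all modest:

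- Some treatment days are lost.
- Doses missed because the bottle is empty would appear in the drug log alongside doses missed by choice. Section 13 lists non-compliance with study drug as a reason for discontinuation and gives no threshold or rule to separate the two.
- The gap falls in the days just before a visit. Section 12.4.2 has serum for retinoids drawn at each visit, although Appendix 1 limits blood draws to weeks 8, 16, 24 and 32.

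**Working it through.** **Inputs.** First supply: 30 days (12.4.1). Dosing: twice daily (11.1, 12.4.1). Return: 28 +/- 6 days after Visit 1 (12.4.1). Day 1 of treatment is Visit 1 (12.4.1). Treatment lasts 32 weeks, which is 32 x 7 = 224 days.

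**The plan's own remark.** Latest permitted return: 28 + 6 = 34 days, and 34 > 30. The comment in 12.4.1 is correct.

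**Doses available.** 30 x 2 = 60.

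**Doses needed.** Suppose a man returns D days after Visit 1. He has D - 1 full dosing days in between, plus v doses from the supply on the Visit 1 day, with v = 2, 1 or 0 because the text does not settle it. No dose is counted on the return day. The need is 2(D - 1) + v.

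| Return after (D) | Days late | Need, v = 2 / 1 / 0 | Shortfall in doses | Shortfall in days |
|---|---|---|---|---|
| 28 | 0 | 56 / 55 / 54 | 0 / 0 / 0 | 0 / 0 / 0 |
| 30 | 2 | 60 / 59 / 58 | 0 / 0 / 0 | 0 / 0 / 0 |
| 31 | 3 | 62 / 61 / 60 | 2 / 1 / 0 | 1 / 0.5 / 0 |
| 32 | 4 | 64 / 63 / 62 | 4 / 3 / 2 | 2 / 1.5 / 1 |
| 33 | 5 | 66 / 65 / 64 | 6 / 5 / 4 | 3 / 2.5 / 2 |
| 34 | 6 | 68 / 67 / 66 | 8 / 7 / 6 | 4 / 3.5 / 3 |

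**Where the gap starts.** It starts at D = 31 if any supplied dose is used on the Visit 1 day, and at D = 32 if none is. Of the 13 permitted return days (22 to 34), 4 or 3 are affected. These are counts of permitted days, not probabilities of a gap.

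**Most lenient count.** Read the latest visit as study day 34 with Visit 1 as day 1 (so D = 33), and take v = 0. The need is 2 x 32 = 64, short by 4 doses or 2 days. The supply falls short on every reading.

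**Size of this one gap.** 3/224 = 1.3% and 4/224 = 1.8% of the treatment period.

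**Check of the remedies.** 34 x 2 = 68 doses meets the need of 68, 67 or 66 at D = 34. With 60 doses, D = 30 (+2 days) is covered for every v. D = 31 (+3 days) is covered only for v = 0 (60 doses), since v = 1 needs 61 and v = 2 needs 62.

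**The case against.** The strongest reply is that this is known and harmless. The protocol flags the shortfall itself, so only the day count and the link to 11.1 are added here. A site that follows 11.1 could dispense to the booked date and avoid the gap. The gap falls about 28 weeks before the week-32 endpoint. If the visit-day rule means no drug at all on those days, the protocol already plans 7 drug-free days, one at each of Visits 2 to 8. That is more than the 3-day gap on the same reading. The preferred remedy also depends on a dispensing limit that the documents do not state.

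Most of this stands as a limit on importance, and none of it removes the contradiction. A flagged problem is still unfixed: staff who follow 12.4.1 as written will dispense 30 days. Section 11.1 states the aim, but the specific instruction defeats it for a late return. The unknown limit is a reason to check before amending and to have a fallback ready.

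**Conclusion.** The point holds as a minor one. Sixty doses are dispensed against 66 to 68 needed at the latest permitted return, leaving up to 3 to 4 days without drug, or 2 on the most lenient count. It affects only men who return about 3 or more days late. The result assumes full adherence and no refill between visits; because it concerns the first supply, it needs no assumption about leftover drug. No sample-size, alpha or power input changes.

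A reader might infer more than the documents support:

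- **A recurring gap, or a total over 32 weeks.** This cannot be computed. The later monthly supply has no day count. Section 12.4.2 collects unused drug at week 32 or early exit, but its sentence on returning drug at other visits ends in a question mark, and Appendix 1 marks collection under T2-T9. Any total also requires later visits to be timed from Day 1. So 1.8% describes the first gap and does not bound the total.
- **A need to narrow the week-8 window.** This rests on the same unsettled points and on whether doses are taken on visit days.
- **Damage to the week-32 result or the retinoid regressions.** An early gap of this length is unlikely to matter at week 32. For the regressions in section 14, the documents give no size of effect, do not say which visit defines the change in serum level, and disagree on whether week 4 is sampled at all.

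**What to change.** 1. First check the dispensing limit. Section 11.1 says "All subjects will be registered in iPLEDGE and undergo the extensive counselling recommended by this program", but the documents do not give the programme's supply rules.
2. If more than 30 days is allowed, change 12.4.1 to dispense at least 34 days (68 doses) at Visit 1.
3. If it is not, keep 30 days and limit the late side of the week-4 window to +2 days, or +3 if the protocol states that no supplied dose is used on the Visit 1 day. This closes the week-4 gap only. Later visits should be rechecked once visit-day dosing is settled.
4. In 12.4.2, state that unused drug is counted and returned to the subject until week 32 or early exit, align the collection row of Appendix 1 with that, and define the later monthly supply as 30 days.
5. Delete the drafting note in 12.4.1.

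With item 2, the cost is a wording amendment and 68 - 60 = 8 extra doses per man, once, or 8 x 20 = 160 doses for the trial. With item 3 there is no extra drug, but the late side at week 4 shrinks from 6 days to 2 or 3, and a man who cannot meet it is out of window.
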